### **5.6.3 Prohibited Concomitant Drugs**

The following treatments will be prohibited for 24 hours after the start of study drug administration:

- 1) Thrombolytic drugs (urokinase, rt-PAs)
- 2) Dual antiplatelet therapy (DAPT)
- 3) Antiplatelet drugs (excluding aspirin and clopidogrel)
- 4) Drugs that inhibit platelet aggregation
- 5) Anticoagulant drugs (excluding enoxaparin and heparin used during

thrombectomy device treatment)

**Table 5.6-1 Prohibited Concomitant Drugs**

Drug Type	Drug Name (Examples)
1) Thrombolytic drugs	Urokinase, t-PAs, etc.
2) Dual antiplatelet therapy	-
3) Antiplatelet drugs	Prasugrel hydrochloride, ticlopidine hydrochloride, ozagrel sodium, ozagrel hydrochloride, cilostazol
4) Drugs that inhibit platelet aggregation (including acidic nonsteroidal anti-inflammatory drugs)	PGE 1 preparations, PGI 2 preparations, ethyl icosapentate, sarpogrelate hydrochloride, dipyridamole, trapidil, dilazep hydrochloride, trimetazidine hydrochloride, etc. Loxoprofen sodium hydrate, indometacin, diclofenac sodium, mefenamic acid, ibuprofen, etc.
5) Anticoagulant drugs	Warfarin, dabigatran, rivaroxaban, apixaban, batroxobin, fondaparinux, argatroban, gabexate mesilate, nafamostat mesilate, freeze-dried concentrated human antithrombin III, freeze-dried concentrated human activated protein C, etc.

**<Rationale>**

- 1) A bleeding risk associated with the combined use of a thrombolytic drug and DS-1040b cannot be ruled out.
- 2) The bleeding risk during DAPT is unknown, although the combined use of an antiplatelet drug (aspirin or clopidogrel) and DS-1040b is likely to be highly safe based on the following study results:
  - ✓ No prolongation of bleeding time was observed, as shown by bleeding time measurement using the Surgicutt method, in Study DS1040-A-E102, in which healthy adults received aspirin 300 mg for 4 days, followed by coadministration of aspirin 300 mg and DS-1040b 6 mg (30-minute intravenous infusion) on Day 5.
  - ✓ No prolongation of bleeding time was observed, as shown by bleeding time measurement using the Surgicutt method, in Study DS1040-A-E106, in which healthy adults received clopidogrel (at loading and maintenance doses of 300 mg and 75 mg, respectively) for 5 days, followed by coadministration of clopidogrel 75 mg and DS-1040b 20 mg (12-hour intravenous infusion) on Day 6.
- 3) 4) 5) A bleeding risk associated with the combined use with DS-1040b cannot be ruled out.

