### 3. STUDY DESIGN

#### 3.1 Overall Design

This study is a multicenter, single-blind, placebo-controlled, randomized, intergroup ascending dose study to confirm the safety and tolerability of DS-1040b in patients with acute ischemic stroke in whom a thrombectomy device is indicated. There will be a total of 4 cohorts, with a planned sample size of 54 or 60 subjects (6 or 12 subjects in the 0.6 mg cohort and 16 subjects per cohort in the other cohorts). The 0.6 mg cohort will only consist of a DS-1040b group. In the other cohorts, subjects will be randomized to the DS-1040b or placebo group in a 3:1 ratio. If any one of the first 6 subjects in the 0.6 mg cohort experiences one event defined as one requiring, “necessary actions to be taken, including discontinuation of the study” as specified in Section 12.4.2, an additional 6 subjects will be enrolled to confirm the safety in a total of 12 subjects. In each cohort, subjects will be evaluated one by one to confirm the absence of symptomatic intracranial hemorrhage through Visit 2 (36 hours after study drug administration) before enrolling the next subject, until 3 subjects aged  $\geq 81$  years are enrolled in the DS-1040b group. In each cohort, safety evaluation will be performed when all data collected through Visit 4 (96 hours after study drug administration) are available to determine whether the study should proceed to the next cohort. Subjects will be required to receive inpatient treatment until Visit 4 at the earliest.

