**Figure 5.1-1 Procedures for Subject Enrollment in Each Cohort**

### 5.1.3 Blinding

This study will be conducted as a single-blind study, in which subjects will be blinded.

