#### **10.4.4 Causality Assessment**

The investigator or subinvestigator should assess causal relationship between an AE and the study drug on the basis of his/her clinical judgment and the following definitions. The causality assessment must be made based on the available information and can be updated as new information becomes available.

Related:

- The AE follows a reasonable temporal sequence from study drug administration, and cannot be reasonably explained by the subject's clinical state or other factors (eg, disease under study, concurrent diseases, and concomitant medications).  
or
- The AE follows a reasonable temporal sequence from study drug administration, and is a known reaction to the drug under study or its chemical group, or is predicted by known pharmacology.

Not Related:

- The AE does not follow a reasonable sequence from study drug administration, or can be reasonably explained by the subject's clinical state or other factors (eg, disease under study, concurrent diseases, and concomitant medications).

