#### **10.4.8 Assessment of Bleeding Adverse Events**

The investigator or subinvestigator will determine whether each AE is a bleeding event, and will record it, with the presence or absence of external factors (with details, if present), in the CRF.

- In case of intracranial hemorrhage

The type of intracranial hemorrhage (symptomatic or asymptomatic), the date/time of the NIHSS assessment (at baseline and onset), and the details of the event will be recorded in the CRF.

- In case of non-intracranial hemorrhage

The presence or absence of a 5 g/dL or greater decrease in hemoglobin, the presence or absence of blood transfusion (with the date/time, name, amount of blood transfusion, and AE(s) requiring blood transfusion, if present), the presence or absence of surgical treatment (with details, if present), and the details of the event will be recorded in the CRF.

The final classification and assessment of bleeding events will be performed by the central adjudication committee member in a blinded fashion. The investigator or

subinvestigator will provide the sponsor with head imaging results used as the basis for assessment.

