### **12.3.3 Safety Analyses**

#### **12.3.3.1 Analysis of Primary Endpoints**

The point estimate and 95% confidence interval of each endpoint listed below will be estimated. Data from the placebo groups of all cohorts will be integrated, whereas data from the DS-1040b groups will be summarized by dose.

- 1) Incidence of symptomatic intracranial hemorrhage (defined by ECASS) within 36 hours after the start of study drug administration
- 2) Incidence of asymptomatic intracranial hemorrhage within 36 hours after the start of study drug administration
- 3) Incidence of non-intracranial (TIMI) major bleeding within 96 hours after the start of study drug administration

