#### **12.4.2 Criteria for Discontinuation or Temporary Discontinuation of the Study**

If any of the criteria specified below are met, the study will be discontinued or temporarily discontinued. Similarly, the study may be discontinued or temporarily discontinued according to these criteria until 3 subjects aged  $\geq 81$  years are enrolled in the DS-1040b group in each cohort.

- 1) If the criterion below is met, the study will be discontinued at that point. After the decision on discontinuation is made, the sponsor will discontinue the study according to the procedures described in Section 16.9:
  - Occurrence of two events of symptomatic intracranial hemorrhage (intracranial hemorrhage with clinical deterioration causing an increase in the NIISS score of  $\geq 4$  points [defined by ECASS]) not attributable to external factors at 36 hours after the start of DS-1040b administration in the DS-1040b group in one cohort
- 2) To ensure the safety of subjects, subject enrollment will be temporarily discontinued and the necessary actions to be taken, including discontinuation of the study, will be considered if any of the criteria listed below are met. If the study is continued based on the results of consideration, subject enrollment will be resumed. If the study is discontinued, the sponsor will discontinue the study according to the procedures described in Section 16.9:
  - Occurrence of one event of symptomatic intracranial hemorrhage (intracranial hemorrhage with clinical deterioration causing an increase in the NIHSS score of  $\geq 4$  points [defined by ECASS]) not attributable to external factors at 96 hours after the start of study drug administration (Visit 4) in the DS-1040b group in one cohort
  - Occurrence of one event of non-intracranial (TIMI) major bleeding at 96 hours after the start of study drug administration (Visit 4) in the DS-1040b group in one cohort
  - Occurrence of any events requiring the consideration of study discontinuation, such as severe hepatic impairment (eg, total bilirubin  $\geq 10$  mg/dL, AST or ALT  $\geq 500$  IU/L, ALP of 5 times the study center’s reference range, bleeding tendency, symptoms of hepatic failure, including consciousness disorder [fulminant hepatitis], hepatic cirrhosis, hepatic tumor, jaundice persisting for

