#### **12.4.3 Criteria**

#### **12.4.4 Data Monitoring Committee**

No data monitoring committee will be established in this study.

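### Is the two-event stopping rule unreliable because external factors are undefined and aspirin study E102 is described in two ways?

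*Combined protocol and SAP*

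**What the plan says.** **Stopping rule.** Section 12.4.2 discontinues the study after two sICH events that are "not attributable to external factors at 36 hours after the start of DS-1040b administration in the DS-1040b group in one cohort". One such event by 96 hours, with the same qualifier, pauses enrollment while action is considered. One non-intracranial TIMI major bleed also causes a pause, with no qualifier about external factors. A further open-ended criterion covers other events that call for considering discontinuation, including treatment-related serious adverse events.

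**Recording and assessment.** Under Section 10.4.8 the investigator decides whether each adverse event is a bleed and "will record it, with the presence or absence of external factors (with details, if present), in the CRF". The same section gives final classification and assessment to a blinded central adjudicator. The causality definition in Section 10.4.4 separately lists "other factors (eg, disease under study, concurrent diseases, and concomitant medications" among possible explanations of an adverse event.

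**Aspirin.** Section 5.6.3 exempts single-agent aspirin and clopidogrel from the 24-hour ban and states no aspirin dose. Its rationale describes E102 as "healthy adults received aspirin 300 mg for 4 days, followed by coadministration of aspirin 300 mg and DS-1040b 6 mg". Section 1.2.1.6 describes a 300 mg loading dose, then 75 mg daily on Days 2 to 5. Sections 1.2.1.6 and 5.6.3 give a 30-minute DS-1040b infusion. Section 5.1.1 calls it 6-hour, with the same Cmax (582 ng/mL) and AUC (1118 h·ng/mL) as Section 1.2.1.6.

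**Related design text.** If one of the first 6 subjects at 0.6 mg has an event that calls for action under Section 12.4.2, then "an additional 6 subjects will be enrolled to confirm the safety in a total of 12 subjects" (Section 3.1). The trial is a "single-blind study, in which subjects will be blinded" (Section 5.1.3), and "No data monitoring committee will be established in this study" (Section 12.4.4). The primary analysis in Section 12.3.3.1 is "Incidence of symptomatic intracranial hemorrhage (defined by ECASS) within 36 hours after the start of study drug administration", with no exclusion for external factors.

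**The concern.** The only mandatory stopping criterion turns on an attribution for which the protocol gives no definition or example. The person who records it is not blinded. Aspirin is a realistic test case, because it may be given inside the 36-hour window and Section 10.4.4 treats concomitant medication as a possible explanation of an adverse event. If one of two sICH events were put down to aspirin, a mandatory stop would become a pause with discretion. In the first 6 subjects at 0.6 mg, the same call on a single sICH could decide whether the cohort grows to 12. The stopping count could also fall below the reported incidence.

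E102 seems to make matters worse. It is the only aspirin interaction study described, and its two accounts disagree on the aspirin dose given with DS-1040b. On that view, nobody could say whether a bleed at a given aspirin dose lay inside or outside the tested combination.

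**Working it through.** **1. The plan's own figure.** Section 12.5 gives 6 or 12 active subjects at 0.6 mg and 16 in each of three further cohorts (12 active, 4 placebo). 6 + 3 × 16 = 54 and 12 + 3 × 16 = 60, so the stated totals reproduce.

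**2. Sensitivity of the rule to set-aside events.** Let p be the true sICH rate and f the share of events set aside for any reason. The counted rate is p(1 − f). For n active subjects:

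- P(two or more) = 1 − (1 − q)^n − nq(1 − q)^(n−1), with q = p(1 − f)
- P(one or more) = 1 − (1 − q)^n

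The inputs are p = 16% (the rt-PA benchmark in Section 12.5) and p = 4.4% (the rate quoted in Section 1.2.2 for patients also treated with a thrombectomy device). The documents give no value for f, so 0 to 0.5 is an assumed range.

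| p | n and event | f = 0 | f = 0.25 | f = 0.5 |
|---|---|---|---|---|
| 16% | 12, two or more | 0.5945 | 0.4314 | 0.2487 |
| 4.4% | 12, two or more | 0.0954 | 0.0577 | 0.0276 |
| 16% | 6, one or more | 0.6487 | 0.5356 | 0.3936 |

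**3. What the table measures.** The f = 0 column describes a rule without the exclusion, which is not the protocol's rule. A precise definition could still leave f above 0. The cost of vagueness is the gap between the share the sponsor intends and the share applied in practice. For illustration, take an intended share of 10% and an applied share of 25%:

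- at 16%: 0.5328 − 0.4314 = 0.1014
- at 4.4%: 0.0795 − 0.0577 = 0.0218

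Both shares are assumptions. Nothing in the documents indicates that such a gap exists, or its direction. The last row of the table also counts only sICH, although TIMI major bleeding and the open-ended criterion can trigger the same expansion.

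**4. Size of the E102 discrepancy.** On the DS-1040b day the ratio is 300/75 = 4. Over five days the totals are 300 + 4 × 75 = 600 mg and 5 × 300 = 1500 mg, a ratio of 2.5.

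**5. Does E102 enter the count?** Section 5.6.3 sets no aspirin dose limit, so neither account of E102 makes a given dose permitted or prohibited. Section 12.4.2 refers to neither aspirin nor E102. Correcting E102 either way leaves the count of every bleed unchanged.

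**6. What happens to an sICH that is set aside.**

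- The open-ended criterion in Section 12.4.2 can still pause enrollment and, through Section 3.1, can still expand the 0.6 mg cohort.
- During the one-by-one phase, Section 12.4.1 bars the next enrollment until absence of sICH over 36 hours is confirmed, with no exception for external factors.
- Section 16.9 lets the sponsor, with the medical expert, consider discontinuation on any information about serious adverse events.
- The event still enters the primary incidence in Section 12.3.3.1.
- External factors are recorded with details, so counts with and without set-aside events can both be produced from data already collected.

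**The case for a change.** The strongest case for a change is that this is the trial's only automatic stop, and discretionary backstops do not restore it. Section 10.4.8 gives the adjudicator the final assessment of bleeds but does not expressly name attribution to external factors. In the synopsis, the adjudication footnote is attached to the hemorrhage term, not to the external-factors phrase. Investigators know the allocation and record the factor. A definition would cost little.

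Some of this stands. The term is undefined for every cause: the procedure, heparin, enoxaparin and clopidogrel as much as aspirin. Attribution is not explicitly assigned. The E102 accounts do contradict one another.

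Three things limit its force. First, the gap touches only the sICH criteria, not TIMI major bleeding or asymptomatic hemorrhage. Second, the route to aspirin borrows a different phrase from a causality rule that Section 12.4.2 does not cite. That rule also has a second limb, under which a well-timed event predicted by the drug's pharmacology is related, with no test for other explanations. A bleed on a profibrinolytic drug could meet that limb despite aspirin. Third, attribution has a working path: recorded details, blinded final assessment, then a cohort decision by the sponsor with the medical expert (Section 12.4.1). Concern about unblinded recording is also weaker for the expansion example, because everyone at 0.6 mg receives active drug.

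**Conclusion.** No change to the design, stopping rule or analysis follows. There are two separate and minor matters.

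The undefined term is missing operational detail of the kind settled case by case by the adjudicator, sponsor and medical expert. An adjudication charter may already define it, and Section 12.4.3, headed as criteria, shows no text in the supplied document. An adjudicator field and a second count would largely repeat the blinded assessment and recorded data already provided for. A primary endpoint broader than a stopping rule is ordinary design, and it means that no sICH within 36 hours drops out of the reported incidence.

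The E102 descriptions in Sections 1.2.1.6, 5.1.1 and 5.6.3 contradict one another on aspirin dose and infusion length and must be reconciled against the study report. This is a clerical correction to supporting text. Every account of the study reports no added prolongation of bleeding time, and no rule, threshold or result depends on which account is right. Nothing here says which that is.

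The fall in stopping probability from 59% to 25% at a 16% rate, or from 9.5% to 2.8% at 4.4%, is illustrative only. It assumes that half of all sICH events are set aside, and it compares the protocol's rule with one that has no exclusion. The cost of leaving the term undefined cannot be estimated from the documents.

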**5.6.4 Other Restrictions**

Elective surgery should not be performed within 5 days after study drug administration (day of study drug administration plus 5 days). However, this does not prevent emergency surgery indicated to treat the subject. The appropriateness of surgery should be determined based on careful assessment of the risks and benefits.

**<Rationale>**

While non-clinical studies as well as clinical studies in healthy adults have shown that DS-1040b does not prolong bleeding time, a possible effect on bleeding has not been ruled out completely. To avoid an unnecessary bleeding risk, non-urgent elective surgery is contraindicated within 5 days after study drug administration. The reason for setting the period of 5 days is that the plasma DS-1040a concentration decreased to less than 10% within 12 hours after the end of the infusion(\*), suggesting that it would have disappeared from the plasma in 5 days.

(\*) Data from Study DS1040-A-U101

## **5.7 Subject Withdrawal/Discontinuation**

### **5.7.1 Reasons for Withdrawal**

If a subject meets any of the following items, the investigator or subinvestigator will immediately withdraw the subject from the study and record the reason for withdrawal in the CRF, and will take appropriate actions for the subject. If abnormalities in test values, etc. are observed at the time of withdrawal, the investigator or subinvestigator will follow the subject's course until such abnormalities have normalized or returned to the baseline level and to an extent that the subject's cooperation can be obtained, perform the medical examinations and tests specified in the protocol, and make all efforts to ensure the subject's safety.

Information of each subject including study completion or withdrawal, date of study completion or withdrawal, and the reason for withdrawal will be recorded in the CRF.

- The subject or his/her legally acceptable representative requests to be withdrawn from treatment.
- The subject receives treatment with any existing thrombolytic drugs (urokinase or rt-PAs) or the need for such treatment arises before or during study drug administration.
- Treatment with a stent-type thrombectomy device is no longer required.
- The need for DAPT arises before or during study drug administration.
- Continuation of the study is not judged to be preferable because of an AE.
- The subject misses a hospital visit.
- The subject is found not to meet all of the inclusion criteria or is found to violate any of the exclusion criteria.
- The investigator or subinvestigator deems that continuation of treatment is inappropriate for another reason.

- The sponsor decides to discontinue the study.

### **5.7.2 Withdrawal Procedures**

If a subject is withdrawn from the study, the investigator or subinvestigator will complete and report the observations as thoroughly as possible up to the day of withdrawal including the date of last treatment and the reason for withdrawal.

- If the decision on study discontinuation is made before Visit 2 assessment  
As the assessment at discontinuation, the Visit 2 assessment should be performed within 24 hours to 36 hours after the start of study drug administration.
- If the decision on study discontinuation is made after the completion of Visit 2 assessment but before Visit 4 assessment  
As the assessment at discontinuation, the Visit 4 assessment should be performed within  $96 \pm 12$  hours after the start of study drug administration.

If the study is discontinued after Visit 4, the assessment at discontinuation will not be required.

Follow-up on Visits 5 and 6 will in principle be performed for all subjects, including those withdrawn from the study.

If the subject is withdrawn due to an AE, the investigator or subinvestigator will follow the subject until the AE has resolved or stabilized.

## 6. STUDY PROCEDURES

### 6.1 Screening and Randomization (Prior to the Start of Study Drug Administration)

- Obtain the subject's signature on the informed consent form (ICF).
- At the study center(s) participating in the gene banking research, obtain the subject's signature on the ICF for the gene banking research (which is optional and will be performed by Visit 4).
- Review inclusion/exclusion criteria.
- Perform head imaging (CT or MRI).
- Record baseline subject characteristics.
- Collect information on complications, concomitant drugs, smoking habit, height, and body weight as far as possible. Any uncollected information should be collected and recorded in the CRF as soon as possible after acute-phase treatment.
- Record the pregnancy test result, as appropriate (the test date and results).
- Record vital signs (blood pressure, pulse rate).
- Perform 12-lead ECG.
- Perform hematology, blood chemistry, and blood coagulation (local) tests.
- Record the baseline NIHSS score.
- Collect blood for the blood coagulation test, and pharmacodynamic and pharmacokinetic assays performed at the central laboratory.

### 6.2 Visit 1 (Day of Study Drug Administration)

- Administer the study drug, and record the start and end times of study drug administration
- Perform thrombectomy device treatment, and record the details (refer to Section 6.19 "Cerebral Artery Revascularization").
- After the completion of thrombectomy device treatment, record the TICI grade and the NIHSS score obtained immediately after the treatment.
- Collect and record information on AEs and any intervention for the AEs (drug and non-drug therapy).
- Record concomitant drugs.
- Perform hematology, blood chemistry, and blood coagulation (local) tests at 6 hours (-5 minutes) after the start of study drug administration, and record the test results.
- Collect blood for a blood coagulation test performed at the central laboratory at 6 hours (-5 minutes) after the start of study drug administration.
- Collect blood for pharmacodynamic assay at 6 hours (-5 minutes) after the start of

study drug administration.

- Collect blood for pharmacokinetic assay at 0.5 hours (-5 minutes), 3 hours ( $\pm 10$  minutes), and 6 hours (-5 minutes) after the start of study drug administration. Collect blood at 18 hours ( $\pm 10$  minutes) after the start of study drug administration as far as possible.
- Collect urine for 24 hours after the start of study drug administration for pharmacokinetic assay.

